1. Patients will come to the Emergency Department or the POC after a supracondylar fracture or periprosthetic distal femur fracture. 2. If they fit all the inclusion and none of the exclusion criteria they will be told about the study either before their surgery if they are lucid, not in pain and can understand the study, or after their surgery when they are lucid, not in pain and can understand the study. If they are not lucid, are in pain, or cannot understand the study during this time they will not be offered participation in the study. 3. They will be told about the study with the understanding that assignment to either partial weight bearing or full weight bearing is standard of care and that physical therapy will conduct the therapy based on their group assignment 4. All questions will be answered and the subject will be given the opportunity to consent 5. They will have a metabolic bone work up done if they are 65 years of age or older which is standard of care. 6. Radiographs will be taken at 6 weeks, 3, 6 and 12 months to determine radiographic healing and/or complications with hardware which is standard of care. 7. Two independent surgeons will review radiographs to determine bridging of 3 or 4 cortices 8. We will measure time to ambulation at 2 weeks, 6 weeks and 3 months. Other variables measured include: Age, gender, date of surgery, Surgeon, Rt/Left, plate (LISS or Locking), smoking status, co-morbidities, perambulatory status, PT participation, time to discharge, discharge disposition, return to baseline ambulation, time to union, pain, Knee society score, knee flexion, radiographic evidence of healing, non-union, malunion, infection, DVT, PE, implant failure/reoperation, Vit D level, death. 9. Patients will complete a health progress report at 2 weeks, 3, 6, and 12 months post-surgery which is standard of care.

Please describe the investigational procedures that will be performed throughout the duration of the study.

Reviewing who heals faster with better outcomes based on assignment to full or partial weightbearing, both of which are standard of care, but for the study, the subject is assigned to one or the other.

Please describe the standard of care procedures that will be performed throughout the duration of the study.

Surgery and anything associated with it.

Will you be assigning or randomizing participants to groups or conditions (e.g., control, placebo)?

Yes

Describe the group assignment.

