We will be looking at two groups: those with periprosthetic distal femur fracture and those with a distal femur fracture proximal to the native knee. Both will have had their distal femur fracture repaired per standard of care. Patients in both groups will then be randomized into two groups: those allowed to bear weight immediately post operatively and those with protected weight bearing post operatively.

Does the research involve surveys/interviews/questionnaires? If so, attach a copy of the interview/survey questions on the Notes & Attachments page.

No

Describe what is known about this topic and why this study is needed. Please include at least two reference citations to support your rationale.

This study is designed to examine if immediate weight bearing on a distal femur fracture fixed with a primary locking plate, either a distal condylar locking plate or a LISS (less invasive stabilization system), is safe and promotes more rapid fracture healing. Historically and currently patients are kept partial weight bearing after fixation of these fractures for 6-12 weeks until callous formation is observed on radiographs. Our hypothesis is that patients that are allowed to bear weight immediately will heal at least as quickly as those that have their weight bearing status protected with the added benefits from early mobilization. Fracture healing will be monitored closely by follow up appointments and complications will be documented. See Lit Review under Notes and Attachments for Scientific Rationale and references.

What method are you going to use to analyze the data?

Descriptive statistics will be performed on the following variables in both groups: Age, gender, date of surgery, Surgeon, Rt/Left, plate (LISS or Locking), smoking status, co-morbidities, perambulatory status, PT participation, time to discharge, discharge disposition, return to baseline ambulation, time to union, pain, Knee society

score, knee flexion, radiographic evidence of healing, non-union, malunion, infection, DVT, PE, implant failure/reoperation, Vit D level, death.

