### Subjects

Indicate the maximum number of subjects to be enrolled or medical records to be reviewed at all sites by the WVU or VAMC research team.

150

Provide a rationale for choosing your sample size.

75 in each group provides 80% power to detect a difference between the groups.

State the requirement(s) to become a participant in the study (e.g., age range, sex, language spoken, class enrollment/ranking).

All patients aged > 18 yo with a distal supracondylar femur fracture will be included, both male and female; Supracondylar distal femur fractures treated with a locked plate, either a distal condylar locking plate or a LISS (less invasive stabilization system), including peri-prosthetic fractures. CPT code 27511

Explain why selection of participants will be equitable addressing gender, ethnicity, and/or race of subjects.

Patients with an intracondylar split, polytrauma patients with associated trauma that will inhibit their ability to weight bear, metastatic disease, incomplete follow up, those with questionable ability to bear weight (ie advanced dementia), open fractures with bone loss, will not be included. Those who are in pain, not lucid, or unable to understand the study at time of consent will not be included.

In outline format and chronological order, describe what will be done to identify and recruit participants (e.g., A, B, C or 1, 2, 3).

1. Patients will come to the Emergency Department or the POC after a supracondylar fracture or periprosthetic distal femur fracture. 2. If they fit all the inclusion and none of the exclusion criteria they will be told about the study either before their surgery if they are lucid, not in pain and can understand the study, or after their surgery when they are lucid, not in pain and can understand the study. If they are not lucid, are in pain, or cannot understand the study during this time they will not be offered participation in the study.

Will any of the subjects be less than 18 years old?

No

Will your study target populations such as pregnant women, fetuses, neonates, or any groups likely to be vulnerable to coercion or undue influence such as children, prisoners, individuals with impaired decision-making capability or economically or educationally disadvantaged persons?

No

Does this research involve participants who could be coerced or unduly influenced, such as current students/employees of research team members?

No

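### Incomplete follow-up is listed as an exclusion, but it cannot be known at screening; applied as written it removes randomised patients for events after assignment.

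*Combined protocol and SAP*

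**What the plan says.** The exclusions appear in the Subjects section, in the answer to the question on equitable selection. Among the patients to be left out are those with "metastatic disease, incomplete follow up, those with questionable ability to bear weight". The term is not defined.

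The recruitment steps in the same section fix when the exclusions are applied: "If they fit all the inclusion and none of the exclusion criteria they will be told about the study", either before surgery or after it. The procedures in the Design section and the Consent Procedures section say the same.

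The group-assignment text in the Design section then states: "Patients in both groups will then be randomized into two groups", meaning immediate or protected weight bearing. On follow-up, the procedures state: "Radiographs will be taken at 6 weeks, 3, 6 and 12 months". Health progress reports also run to 12 months after surgery.

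The analysis is described as descriptive statistics in both groups, on a list of variables that ends with "non-union, malunion, infection, DVT, PE, implant failure/reoperation, Vit D level, death". Nowhere do the documents define an analysis population, a way of handling missing data, or the treatment of patients who die.

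**The concern.** The other conditions in the exclusion list, such as an intracondylar split, metastatic disease or an open fracture with bone loss, can be judged at presentation or around surgery. Completeness of follow-up cannot. It becomes known only as the 12 months pass, after the patient has been assigned to an arm.

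A rule that leaves out such patients therefore turns the randomised comparison into a comparison of completers. Randomisation makes the arms comparable at assignment. It does not make the patients who remain at month 12 comparable if the reasons for leaving are related to outcome and differ by arm. Patients and physical therapists know the assignment, so losses that differ by arm are plausible, although the documents give no loss rates.

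The stakes are highest for safety. The trial asks whether immediate weight bearing is safe, and death is one of its outcomes. A patient who dies before the last visit has, on the natural reading, incomplete follow-up, so the plan both records the death and excludes the patient. Non-union and implant failure or reoperation are affected less directly: a patient with either who attends every visit is kept, but these patients may be lost more or less often than others. The rule would also discard usable data, such as 6-week and 3-month films from a patient who misses month 12.

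**Working it through.** **1. Timing.** This step needs no figures.

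| Step | When | Source |
|---|---|---|
| Exclusions checked | Before the study is offered, around surgery | Subjects; Design; Consent Procedures |
| Assignment to arm | After eligibility and consent | Design, group assignment |
| Last film and last health report | 12 months | Design, procedures items 6 and 9 |

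The first row cannot use information from the third. The item is therefore either without effect at screening or applied after assignment.

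**2. Effect on observed rates.** The documents give no event or loss rates, so every rate here is an assumption. Let p be the true failure risk in an arm, Lf the proportion of failures lost and Ls the proportion of other patients lost. Among patients kept,

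observed risk = p(1 − Lf) / [p(1 − Lf) + (1 − p)(1 − Ls)].

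Example: p = 0.25, Lf = 0.4, Ls = 0.1 gives 0.150 / (0.150 + 0.675) = 0.182.

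Assume true risks of 15% (protected) and 25% (immediate), a difference of 10 points. The true odds ratio is (0.25/0.75) / (0.15/0.85) = 1.89.

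| Pattern | Loss assumed | Protected | Immediate | Difference (points) | Odds ratio |
|---|---|---|---|---|---|
| a | Failures 40%, others 10%, both arms | 10.5% | 18.2% | 7.7 | 1.89 |
| b | Failures 10% protected, 40% immediate; others 10% | 15.0% | 18.2% | 3.2 | 1.26 |
| c | Failures 40% protected, 10% immediate; others 10% | 10.5% | 25.0% | 14.5 | 2.83 |
| d | Failures 10%, others 40%, both arms | 20.9% | 33.3% | 12.4 | 1.89 |

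In a and d the loss pattern is the same in both arms, so the odds ratio is unchanged and only the arm rates and the risk difference move. In b and c the odds ratio moves too. If Lf and Ls may each be 10% or 40% in each arm (16 combinations), the apparent difference runs from 18.2 − 20.9 = −2.7 points to 33.3 − 10.5 = +22.8 points.

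**3. No true difference.** Assume 20% failure in both arms and 75 randomised per arm, so 15 failures and 60 others in each.

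- Arm losing 40% of failures and 10% of others: 9 failures among 9 + 54 = 63 kept, or 14.3%. Total loss is 12/75 = 16%.
- Arm losing 10% of both: 13.5 among 67.5 kept, or 20.0%. Total loss is 10%.
- False difference: 5.7 points.

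If these completers were compared by a two-sided 5% test of proportions (normal approximation), the pooled rate would be 22.5/130.5 = 0.172. The null standard error is √[0.172 × 0.828 × (1/63 + 1/67.5)] = 0.066, and the critical difference is 1.96 × 0.066 = 0.130. The unpooled standard error is also 0.066. The chance of a false positive is then about 13.7%. With 30% of failures lost instead of 40%, the figures are 16.3% v 20.0% and about 8.5%. The plan specifies no test, so these error rates are only a scale for the bias.

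**4. Loss unrelated to outcome.** There is then no bias, only lost precision. The plan's 75 per group with 80% power cannot be reproduced, because no endpoint, effect size or significance level is given. Assuming that group means arm, a two-sided 5% level and a comparison of means, 75 per arm corresponds to a difference of (1.960 + 0.842) × √(2/75) = 0.457 SD. If 20% are removed, leaving 60 per arm, power is Φ(0.457 × √(60/2) − 1.960) = about 71%.

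**The case against.** The strongest reply concerns what the phrase means. The documents give a single point at which exclusions are applied, before the study is offered, and nothing says that they are re-applied later or that data are deleted. On that reading the item excludes nobody and does no harm. Alternatively, since the rest of the list is judged at baseline, the author may have meant patients not expected to return. Listing death as a variable to be described also suggests that deaths were not meant to be dropped.

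These readings are possible, but no passage states either of them. The words describe follow-up that is incomplete, not follow-up expected to be so. They are also the plan's only instruction on what to do with a patient who is lost, and an analyst following them would leave that patient out.

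Three narrower points stand. The direct contradiction is with death; for non-union and reoperation the problem is a possible association with loss. The numerical range reflects the loss rates chosen and shows that bias can arise, not how large it would be here. And any analysis of available data also faces loss to follow-up, although it keeps the early films and events that a completers-only rule discards.

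**Conclusion.** The concern holds and the text is wrong as written. The finding rests on timing and needs no outside figure: completeness of 12-month follow-up cannot be an eligibility criterion checked around surgery, and the rule can take effect only by removing patients after assignment. Nothing else in the plan protects the comparison.

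The size and direction of any bias cannot be derived from the documents. Under the assumed loss rates of 10% or 40%, a true 10-point difference could appear as anything from −2.7 to +22.8 points, and a true null as a 5.7-point difference. If loss is unrelated to outcome, the cost is precision only. Whether any patient has been dropped under the rule is not stated. The item must be corrected because it is a stated rule that, if followed, undermines a randomised safety comparison, and correcting it is cheap.

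**What to change.** Delete incomplete follow-up from the exclusions in the Subjects section. If patients not expected to return were meant, state that as a criterion that can be judged at consent.

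Add to the analysis text in the Design section:

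- Every randomised patient is analysed in the assigned arm, using all available visits.
- All deaths and reoperations are counted in the safety table, whatever the length of follow-up.
- Completeness of follow-up and reasons for loss are reported by arm.

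For time to union, patients with partial follow-up should be kept as censored. Union is seen only at the scheduled films, so an interval-censored method is suitable. Treating death as a competing event is optional. These two refinements are secondary to the changes above.

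The cost is a short amendment and a little more analysis work, with no extra patients or visits. The Protocol Notes record a renewal in 2019; if patients have already been dropped under this rule, recovering their data would take further work.

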### **Consent Procedures**

Will SIGNED informed consent be obtained from subjects (paper-based and/or electronic)?

Yes

Will the informed consent form be translated into any other language(s)?

No

Is a waiver of informed consent being requested (i.e., there will be no consent process at all)?

No

Is a waiver of the requirement to obtain written documentation of the consent process being requested (if yes, attach the information to be provided to the participants)?

No

Are you requesting an alteration of consent (e.g., short form, braille consent or witnessed verbal consent)?

No

For remote or in-person electronic consent, complete an e-IC worksheet from the [OHRP Forms page](#) and attach it to the submission.

If only paper-based in-person consent will be used, describe the consent process. Address the following separately:

1. When will prospective participants be approached for consent?
2. Where will the consent occur?
3. How will the research and the consent materials be explained, and how and when will questions be answered?

. Patients will come to the Emergency Department or the POC after a supracondylar fracture or periprosthetic distal femur fracture. 2. If they fit all the inclusion and none of the exclusion criteria they will be told about the study either before their surgery if they are lucid, not in pain and can understand the study, or after their surgery when they are lucid, not in pain and can understand the study. If they are not lucid, are in pain, or cannot understand the study during this time they will not be offered participation in the study. 3. They will be told about the study with the understanding that assignment to either partial weight bearing or full weight bearing is standard of care and that physical therapy will conduct the therapy based on their group assignment 4. All questions will be answered and the subject will be given the opportunity to consent.

Indicate who will be consenting subjects and describe the process of training all personnel who will be obtaining consent.  
Research coordinators may consent subjects. They have been trained and have been conducting the consent process for years.

### **Potential Benefits**

Is there any known benefit to the individual subject as a result of participating in the research? Payments to subjects should not be included in this section, but addressed in the Payments/Reimbursements section.

If our hypothesis is correct, those subjects who do full weight bearing will heal faster and suffer less complications.

Describe the potential benefit(s) to society and/or scientific / medical knowledge of the planned work.

Understanding and sharing information gathered from the research study re: benefit or no benefit to full weight bearing after a supracondylar distal femur fracture.

### **Confidentiality**

At any point during this study, will identifiable data be viewed or recorded?

Yes

Data must be kept for a minimum of three (3) years after study completion. In addition to the required 3 years, how much longer will the data be kept?  
no longer than 3 years

Where will data be securely located?

On a coded spreadsheet, on the password protected computer of a research team member in the Dept of Orthopaedics.

How will data be destroyed?

Erasing it from the computer.

Will anyone other than the PI, research team members, or IRB have access to the identifiable data (e.g., sponsor/funding source, other collaborators)?

No

Describe the steps that will be taken to maintain the privacy of subjects (e.g., where interaction takes place) and the confidentiality of data (e.g., master code).

A coded spreadsheet has been developed onto which all the data gathered will be placed. An identifier spreadsheet has been developed and will be kept separate from the coded spreadsheet.

Does this study have a Federal Certificate of Confidentiality? If yes, attach the certificate on the Notes & Attachments page.

No

**Financial Considerations**

Will the subjects incur any costs to participate in this project (e.g., travel, physician fees, study procedures, study drugs)?  
No

Will the subject be paid (money, gift certificates, coupons, etc.) to participate in this research project?  
No

Will WVU students receive extra credit for participating in this research project?  
No

**Advertisements**

Will there be advertisements for this study?  
No

**Sample Collection**

Will sample(s) be used?  
No

**Biological Safety**

Does the study involve the handling of any infectious and/or non-infectious agents or recombinant DNA?  
No

**Data Protection for IRB**

Does the project have data protection requirements?  
No

## Protocol Notes

DATE	AUTHOR	TOPIC	NOTE
09/10/2019 02:45 PM	[name]	A004	add study personnel [name]
09/05/2019 03:22 PM	[name]	response to revisions	retired study personnel have been removed from ICF
08/23/2019 02:09 PM	[name]	renewal 05	removed a study personnel due to retirement
06/18/2015 04:25 PM	[name]	amendment	
the following changes have been made to Design/Procedures, Consent Procedures, and the Consent form: 1. Patients will come to the Emergency Department or the POC after a supracondylar fracture or periprosthetic distal femur fracture. 2. If they fit all the inclusion and none of the exclusion criteria they will be told about the study either before their surgery if they are lucid, not in pain and can understand the study, or after their surgery when they are lucid, not in pain and can understand the study. If they are not lucid, are in pain, or cannot understand the study during this time they will not be offered participation in the study. 3. They will be told about the study with the understanding that assignment to either partial weight bearing or full weight bearing is standard of care and that physical therapy will conduct the therapy based on their group assignment 4. All questions will be answered and the subject will be given the opportunity to consent 5. They will have a metabolic bone work up done if they are 65 years of age or older which is standard of care. 6. Radiographs will be taken at 6 weeks, 3, 6 and 12 months to determine radiographic healing and/or complications with hardware which is standard of care. 7. Two independent surgeons will review radiographs to determine bridging of 3 or 4 cortices 8. We will measure time to ambulation at 2 weeks, 6 weeks and 3 months. Other variables measured include: Age, gender, date of surgery, Surgeon, Rt/Left, plate (LISS or Locking), smoking status, comorbidities, perambulatory status, PT participation, time to discharge, discharge disposition, return to baseline ambulation, time to union, pain, Knee society score, knee flexion, radiographic evidence of healing, non-union, malunion, infection, DVT, PE, implant failure/reoperation, Vit D level, death. 9. Patients will complete a health progress report at 2 weeks, 3, 6, and 12 months post-surgery which is standard of care. Consent form: Under Purpose: You will have or have had surgery to repair Under Description of Procedures: removed 'except for the 2 week follow up.

